16.3 Efficacy Analysis for Phase II

All patients who have received a minimum of 1 cycle of study treatment, had baseline assessments

and at least one on-study tumor assessment will be considered evaluable for response.

Response rate is defined as the proportion of patients with a Complete (CR) or Partial Response (PR) relative to the total number of evaluable patients. Responses will be defined according to the RECIST version 1.1 guidelines for solid.

The best overall response is the best response recorded from the start of treatment until disease progression/recurrence (taking as reference for progressive disease the smallest measurements recorded since the treatment started) or the withdrawal from the study. Stable disease will be considered the best response when observed at least after two months from baseline. Tumor responses will be analyzed in a descriptive manner. The number and percentage of objective response (CR+PR) will be tabulated. Response rate may be summarized with the corresponding 95% exact confidence interval.

Progression free survival will be defined as the number of days between the first treatment with protocol specified therapy and death or progression, whichever comes first. Individuals who are alive and progression free at last contact will be censored at that time.

Overall survival (OS) will be defined as the number of days between the first treatment with protocol specified therapy and death. Individuals who are alive at last contact will be censored at that time.

Progression free survival and overall survival time distributions in the Phase II study population will be summarized using the methods of Kaplan and Meier.

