Duration of therapy will depend on individual response, evidence of disease progression and tolerance.

In the absence of treatment delays due to adverse event(s), treatment with nivolumab may continue as indicated in each cohort or until one of the following criteria applies:

- Disease progression (see information on patients remaining on study post progression)
- Intercurrent illness that prevents further administration of treatment
- Unacceptable adverse event(s)

- Participant demonstrates non-compliance with treatment regimen and/or required study evaluations
- Participant decides to withdraw from the protocol therapy
- General or specific changes in the participant's condition render the participant unacceptable for further treatment in the judgment of the treating investigator
- Any required toxicity reason as noted in prior sections of the protocol requiring the patient stop treatment
- Any adverse event, laboratory abnormality, or intercurrent illness which, in the judgment of the Investigator, presents a substantial clinical risk to the subject with continued nivolumab dosing
- Oncoceutics decision to forgo further drug development of ONC201

Participants will be removed from the protocol therapy when any of these criteria apply. The reason for removal from protocol therapy, and the date the participant was removed, must be documented in the case report form (CRF). Alternative care options will be discussed with the participant.

10 Efficacy Evaluations

Tumor assessment for solid tumors will include all known or suspected disease sites. Imaging may include chest, abdomen and pelvis CT or MRI scans (when applicable); brain CT or MRI scan for patients with known brain metastases or those with suspected brain metastases; bone scan and/or bone x-rays for patients with bone metastases, if applicable. CT (or MRI) of chest, abdomen and pelvis, will be used for response.

Antitumor activity for patients with solid tumors will be assessed through radiological tumor assessments conducted at baseline, at the end of every other cycle (every 8 weeks), whenever disease progression is suspected (e.g., symptomatic deterioration), and at the time of withdrawal from the study (if not done in the previous 4 weeks).

Assessment of response in these patients will be made using RECIST version 1.1. All patients' files and radiologic images must be available for source verification.

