For patients who continue treatment in the case of initial radiologic progression, a repeat CT scan will be obtained within 8 weeks (± 7 days) of the initial detection of PD to determine whether there has been a decrease in the tumor size or further progression, defined as an additional 10% increase in tumor burden from time of initial PD. This includes an increase in the sum of diameters of all target lesions, increase in the sum of the diameters of new measurable lesions compared to the time of initial PD, and/or unequivocal progression in non-target lesions (compared to the time of initial PD).

- **Study treatment should be discontinued permanently upon documentation of further progression.**
If patient has **not** additional progression (10%) they can stay on treatment and continue on with study imaging as per the protocol time frames. However, if they subsequently progress by 10% at any time after, they must come off study.
- If SD is documented, patients will be allowed to continue on study treatment. However, if they subsequently progress by 10% at any time after, they must come off study.
For patients who experience a PR or CR (compared to baseline CT), they will continue treatment. They will be recorded as a **delayed response**

Definitions

Evaluable for Target Disease response. Only those participants who have measurable disease present at baseline, have received at least one cycle of therapy, and have had their disease re-evaluated will be considered evaluable for target disease response. These participants will have their response classified according to the definitions stated below. (Note: Participants who exhibit objective disease progression prior to the end of cycle 1 will also be considered evaluable.)

Evaluable Non-Target Disease Response. Participants who have lesions present at baseline that are evaluable but do not meet the definitions of measurable disease, have received at least one cycle of therapy, and have had their disease re-evaluated will be considered evaluable for non-target disease. The response assessment is based on the presence, absence, or unequivocal progression of the lesions.

Disease Parameters

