Note: Participants with a global deterioration of health status requiring discontinuation of treatment without objective evidence of disease progression at that time should be

reported as “*symptomatic deterioration*.” Every effort should be made to document the objective progression even after discontinuation of treatment.

For Participants with Non-Measurable Disease (i.e., Non-Target Disease)

Non-Target Lesions	New Lesions	Overall Response
CR	No	CR
Non-CR/non-PD	No	Non-CR/non-PD*
Not all evaluated	No	not evaluated
Unequivocal PD	Yes or No	PD
Any	Yes	PD

* ‘Non-CR/non-PD’ is preferred over ‘stable disease’ for non-target disease since SD is increasingly used as an endpoint for assessment of efficacy in some trials so to assign this category when no lesions can be measured is not advised

Modified immune-related response criteria (irRC), derived from RECIST 1.1

This irRC classification is based on the recent learning from clinical studies with cancer immunotherapies that even if some new lesions appear at the beginning of a treatment or if the total tumor burden does not increase substantially, tumor regressions or stabilizations might still occur later. The irRC were created using bidimensional measurements (as previously widely used in the World Health Organization criteria). For this trial, the concepts of the irRC are combined with RECIST 1.1 to come up with the modified irRC.

For modified irRC, only target and measurable lesions are taken into account. In contrast to the RECIST 1.1 criteria, the modified irRC criteria (a) require confirmation of both progression and response by imaging at 8 weeks after initial imaging and (b) do not necessarily score the appearance of new lesions as progressive disease if the sum of lesion diameters of target lesions (minimum of 10 mm per lesion, maximum of 5 target lesions, maximum of 2 per organ) and measurable new lesions does not increase by $\geq 20\%$.

The same method of assessment and the same technique should be used to characterize each identified and reported target lesion(s) at baseline, during the trial, and at the end of trial visit. All measurements should be recorded in metric notation. The modified irRC based on RECIST 1.1 are displayed below.

Modified immune-related response criteria are defined as follows:

New measurable lesions: Incorporated into tumor burden.

New non-measurable lesions: Do not define progression but precludes (irCR).

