16.4 Primary Analysis for Phase II

Following completion of the Phase I trial, we will conduct a single-arm, double endpoint Phase II study to evaluate the efficacy of the promising treatment combination. In Phase II, we will evaluate the co-primary outcomes of response and Progression Free Survival (PFS), testing the composite null hypothesis that P_r , the chance of response, is at most 5% AND the chance of PFS at 3 months, P_s , is at most 50%. The alternative for which power is computed is that the P_r is at least 20% OR P_s is at least 71% (this corresponds to median PFS of 6 months, assuming an exponential model). Our double end-point design (Sill *et al.*, 2012) evaluates an initial cohort of 17 patients. If 1 of 17 respond or 4/17 are Progression Free (PF) at 3 months then recruitment will continue to 34 patients. The null is rejected if there are at least 5/34 responses or at least 22/34 patients PF at 3 mo. Statistics under independence of response and PFS at 3 months (i.e., $P_{rs} = p(\text{response AND PFS at 3 months}) = P_r * P_s$), as well as the most extreme forms of dependence, ($P_{rs} = \min(P_r, P_s)$ or $P_{rs} = \max(0, P_r + P_s - 1)$), were computed. Power: The design provides at least 80% power and at most 7.9% type I error. The chance of early stopping under the null is at least 52% and at most 10.7% under any alternative.

Pharmacokinetic Analysis

All patients who complete at least one day of PK blood sampling will be included in the PK analyses. Plasma concentration/time data of ONC201 obtained at the designated times will be summarized descriptively and presented graphically by dose and day of assessment. The concentration/time data of ONC201 will be analyzed using non-compartmental methods to obtain PK parameters in individual patients. These PK parameters include the maximum plasma

concentration (C_{max}), time to maximum plasma concentration (T_{max}), area under the plasma concentration versus time curve to 24 hours (AUC_{24hr}) and area under the plasma concentration versus time curve to the time of the last measurable concentration (AUC_{last}). If data permit, area under the plasma concentration versus time curve to infinity (AUC_{inf}), terminal elimination half-life ($t_{1/2}$), oral plasma clearance (CL/F) and apparent volume of distribution (Vd/F) will be also estimated.

Individual values and descriptive statistics of these PK parameters will be provided by dose and day of assessment in tabular form.

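### The co-primary response rate is defined over evaluable patients but tested as 5 of 34 treated patients, so the reported rate and its interval can only err upward

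*Combined protocol and SAP*

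**What the plan says.** Response is one of two co-primary outcomes in phase II; the other is being progression-free at 3 months (section 16.4).

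- **Estimate (section 16.3).** The rate is CR plus PR "relative to the total number of evaluable patients". To be in that set a patient needs one or more cycles of therapy, a baseline work-up and a scan during the study; the last condition reads "at least one on-study tumor assessment will be considered evaluable for response". The number and percentage of responders are tabulated, and a 95% exact interval may be added.
- **Test (section 16.4).** "The null is rejected if there are at least 5/34 responses or at least 22/34 patients PF at 3 mo". No analysis population is named. The synopsis (Planned Enrollment), section 4.2 and section 16.2.1 describe the 34 as patients treated at the RP2D; the synopsis and 16.2.1 break this down as 6 from phase Ib plus 28 more.
- **Evaluability (section 10, Definitions).** The requirements are close to those of 16.3 (measurable disease at baseline, one cycle, disease re-evaluated), with an added note: "Participants who exhibit objective disease progression prior to the end of cycle 1 will also be considered evaluable". Section 16.3 does not repeat the note.
- **Scan timing (section 10).** Tumor assessment is due "at the end of every other cycle (every 8 weeks), whenever disease progression is suspected", and at withdrawal if not done in the previous 4 weeks. The section 8 calendar has a matching off-study CT.
- **Stopping without documented progression (section 10).** "Participants with a global deterioration of health status requiring discontinuation of treatment without objective evidence of disease progression" are recorded as symptomatic deterioration.

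**The concern.** The quantity reported and the quantity tested have different denominators. The exclusions from the reported one are not neutral. Patients who stop before completing a cycle, or who die, deteriorate, stop for toxicity or withdraw without a post-baseline scan, are treatment failures for this endpoint, and all of them would be non-responders. Removing them moves the estimate in one direction only.

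Early failure is foreseeable here. Patients have progressed after at least two regimens, ECOG status up to 2 is allowed, and the first routine scan is at week 8.

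In a single-arm trial the response rate and its interval are what a reader sets against the 5% null and the 20% alternative. A rate computed on a reduced set would look better than the result of the plan's own rule, and the report would not show why.

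**Working it through.** **Inputs.** Null response rate 5%, alternative 20%, final rule at least 5/34 (section 16.4). Evaluable definition and optional exact interval (section 16.3). The 34 are patients treated at the RP2D (synopsis, sections 4.2 and 16.2.1). The share not evaluable is not in the documents. I assume 0 to 20%, that is, from 34 down to about 27 evaluable (34 × 0.80 = 27.2).

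**Step 1: the plan's own figures.** Section 16.4 states type I error of at most 7.9%, power of at least 80%, early stopping of at least 52% under the null and at most 10.7% under any alternative. I computed the exact joint distribution of response and 3-month status over two stages, under independence and the two extreme dependences that the section names.

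- With the stage 1 cut-offs as printed (1/17 or 4/17), type I error is 8.2 to 8.6% and early stopping under the null is 0.1 to 0.5%. The stated figures do not reproduce.
- With continuation at 2 or more of 17 responding or 10 or more of 17 progression-free, and the same final rule, type I error is 7.5 to 7.9%, minimum power 79.5%, and early stopping 51.6 to 57.1% under the null and at most 10.7% under an alternative. These match to rounding.

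The stage 1 discrepancy is a separate matter. For this point, what counts is that the stated operating characteristics belong to the final rule with a fixed denominator of 34. Taken alone, the response part of that rule has P(X ≥ 5 | n = 34, p = 0.05) = 2.6% and P(X ≥ 5 | n = 34, p = 0.20) = 83.8%.

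**Step 2: direction.** Let x be the number of responders and m the number evaluable, m ≤ 34. Excluded patients contribute nothing to x, so

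reported rate ÷ all-treated rate = (x/m) ÷ (x/34) = 34/m ≥ 1.

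The exact lower and upper limits both rise as m falls with x fixed.

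**Step 3: size, with 5 responders (Clopper-Pearson 95%).**

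| Evaluable m | 34/m | 5/m | Exact 95% CI |
|---|---|---|---|
| 34 | 1.00 | 14.7% | 4.95 to 31.1% |
| 33 | 1.03 | 15.2% | 5.11 to 31.9% |
| 30 | 1.13 | 16.7% | 5.6 to 34.7% |
| 29 | 1.17 | 17.2% | 5.85 to 35.8% |
| 27 | 1.26 | 18.5% | 6.3 to 38.1% |

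**Step 4: a failing count.** Four responses do not meet the response criterion. They are 4/34 = 11.8% of treated patients but 4/27 = 14.8% of 27 evaluable patients, against 5/34 = 14.7% at the boundary. At 28 evaluable, 4/28 = 14.3%, still below it.

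**Step 5: the test.** The rule counts responses. With 34 treated patients as the base, a patient without a scan adds no response whether labelled evaluable or not, so whether 5 is reached does not change.

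**The case against.** The strongest reply is that this concerns reporting, not the decision. Section 16.4 works on a count, never uses an interval, and the 34 are described as treated; section 16.3 calls the response analysis descriptive and makes the interval optional. That stands, and it limits the point to the estimate and its interval.

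A reader might infer more: that the trial's type I error is inflated. If the rule were applied to 34 evaluable patients, with extra patients enrolled to reach that number, the evaluable-set null rate would be 0.05/(1 − f) for non-evaluable share f. The response-only error would then rise from 2.6% to 3.8% at f = 10% and about 5.9% at f = 20%. The overall error, using the stage 1 cut-offs that reproduce 7.9%, would be about 9.1% and 10.9%. The documents do not support that reading. No section replaces non-evaluable phase II patients; the replacement rule in section 6.4.3 sits in the phase Ib de-escalation rules, and section 16.2.1 fixes 28 additional patients for 34 treated.

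It is also tempting to say that everyone who fails before week 8 is dropped. Section 10 requires scans at suspected progression and at withdrawal, and asks for every effort to document progression after treatment stops. Its note also keeps early objective progressors. If that note governs 16.3, the loss narrows mainly to patients with no post-baseline assessment. It does not vanish: deaths, withdrawals and unscanned deterioration remain, and 16.3 as worded still excludes anyone who stops before completing a cycle.

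Lastly, the lower limit passing 5% between 34 and 33 evaluable (4.95% to 5.11%) is a knife-edge on which no planned decision turns. I give it no weight beyond illustration. The 3-month PFS endpoint carries no evaluability condition, so early failures are not excluded from that outcome.

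**Conclusion.** Wrong as written, for the reported response rate and its confidence interval. The denominator in 16.3 does not match the one tested in 16.4, and the mismatch can only push the reported figures up. The factor is 34/m: nil if every patient is evaluable, 1.03 if one is lost, 1.26 if seven are lost. The size rests on an assumed non-evaluable share of 0 to 20%, because the plan gives none; the direction does not depend on that assumption.

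The conclusion does not extend to the go/no-go decision, provided the 5/34 is counted over treated patients, as the descriptions of the 34 indicate. Section 16.4 should nevertheless say so, since it names no population. Sections 10 and 16.3 also need to be reconciled on patients with objective progression before the end of cycle 1.

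**What to change.** 1. In section 16.3, define the response rate as CR plus PR divided by all patients treated at the RP2D, and state that these are the same 17 and 34 as in section 16.4.
2. Count any patient without a post-baseline tumor assessment as a non-responder.
3. Report the evaluable-set rate as a labelled sensitivity figure, with the number excluded and the reasons.
4. Use one evaluable definition in sections 10 and 16.3, including an explicit statement on objective progression before the end of cycle 1.

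The cost is a sentence or two in each section, with no new data and no change in sample size. The reported response rate may come out slightly lower than under the present wording.

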16.4 Primary Analysis for Phase II

Following completion of the Phase I trial, we will conduct a single-arm, double endpoint Phase II study to evaluate the efficacy of the promising treatment combination. In Phase II, we will evaluate the co-primary outcomes of response and Progression Free Survival (PFS), testing the composite null hypothesis that P_r , the chance of response, is at most 5% AND the chance of PFS at 3 months, P_s , is at most 50%. The alternative for which power is computed is that the P_r is at least 20% OR P_s is at least 71% (this corresponds to median PFS of 6 months, assuming an exponential model). Our double end-point design (Sill *et al.*, 2012) evaluates an initial cohort of 17 patients. If 1 of 17 respond or 4/17 are Progression Free (PF) at 3 months then recruitment will continue to 34 patients. The null is rejected if there are at least 5/34 responses or at least 22/34 patients PF at 3 mo. Statistics under independence of response and PFS at 3 months (i.e., $P_{rs} = p(\text{response AND PFS at 3 months}) = P_r * P_s$), as well as the most extreme forms of dependence, ($P_{rs} = \min(P_r, P_s)$ or $P_{rs} = \max(0, P_r + P_s - 1)$), were computed. Power: The design provides at least 80% power and at most 7.9% type I error. The chance of early stopping under the null is at least 52% and at most 10.7% under any alternative.

Pharmacokinetic Analysis

All patients who complete at least one day of PK blood sampling will be included in the PK analyses. Plasma concentration/time data of ONC201 obtained at the designated times will be summarized descriptively and presented graphically by dose and day of assessment. The concentration/time data of ONC201 will be analyzed using non-compartmental methods to obtain PK parameters in individual patients. These PK parameters include the maximum plasma

concentration (C_{max}), time to maximum plasma concentration (T_{max}), area under the plasma concentration versus time curve to 24 hours (AUC_{24hr}) and area under the plasma concentration versus time curve to the time of the last measurable concentration (AUC_{last}). If data permit, area under the plasma concentration versus time curve to infinity (AUC_{inf}), terminal elimination half-life ($t_{1/2}$), oral plasma clearance (CL/F) and apparent volume of distribution (Vd/F) will be also estimated.

Individual values and descriptive statistics of these PK parameters will be provided by dose and day of assessment in tabular form.

To determine any interactions between ONC201 and nivolumab, plasma concentrations of both drugs will be monitored closely. Changes in PK parameters, such as T_{max} , C_{max} , λ_z , $t_{1/2}$, AUC_{last} , AUC_{inf} , C_{min} and, CL/F, of ONC201 will be compared between single agent ONC201 (run-in component) and ONC201+ nivolumab. Similarly, PK parameters of nivolumab will be compared to historical control (Gaudreault J, Cancer Chemother Pharmacol).

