Phase II: A total of 34 patients will be treated at the RP2D (including 6 patients from the Phase IB treated at the RP2D and 28 patients from phase II). Interim safety analysis after 12 patients accrued at the RP2D, interim efficacy analysis after 17 patients.)

Eligibility Criteria:

Inclusion: Patients aged \geq 18 years must have a histologically/cytologically -confirmed primary MSS colorectal tumors who progressed after at least 2 lines of treatment

Exclusion: Patients with symptomatic brain metastases. Patients with inflammatory and autoimmune diseases or other medical disease in which Nivolumab is contraindicated. Patients with prior ONC201 will be excluded.

Randomization:

This is a single arm study with no randomization. All enrolled patients will receive the study drugs.

Correlative Studies

Pre- and post-treatment biopsies are mandatory to evaluate tumor infiltration of NK, T cells, cancer stem cells. Tumor biopsies will be used to evaluate integrated stress response (ISR), TNF-related apoptosis-inducing ligand (TRAIL), DR5, granzyme, perforin, cell death, cell proliferation. PD-1 and PD-L1 testing will all be performed.

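### The stage-1 futility rule as written stops an inactive regimen 0.1–0.5% of the time, not the stated 52% or more, and type I error exceeds the stated 7.9%

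*Combined protocol and SAP*

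**What the plan says.** Section 16.4 describes a two-stage design with two co-primary endpoints, response and progression-free status at 3 months. The null is a response probability of at most 5% and a 3-month PFS probability of at most 50%. The alternative is that "the P_r is at least 20% OR P_s is at least 71" per cent. Stage 1 "evaluates an initial cohort of 17 patients", and the continuation rule is: "If 1 of 17 respond or 4/17 are Progression Free (PF) at 3 months then recruitment will continue to 34 patients". At the end, the null is rejected with 5 or more responses or 22 or more progression-free patients among 34.

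Two sentences give the operating characteristics, said to cover independence and the two extreme forms of dependence between the endpoints: "The design provides at least 80% power and at most 7.9% type I error" and "The chance of early stopping under the null is at least 52% and at most 10.7% under any alternative".

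The Synopsis (Planned Enrollment) mentions an "interim efficacy analysis after 17 patients" but gives no cut-offs. The boundary appears only in Section 16.4.

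**The concern.** A continuation bar of 4 progression-free patients among 17 is 24%, less than half the 50% rate the plan regards as uninteresting. A regimen with no activity beyond the null would be expected to yield 17 × 0.50 = 8.5. A single response also suffices to continue. A rule this lenient cannot stop half of inactive regimens, so either the cut-offs or the quoted probabilities are wrong.

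This is the sentence on which the go/no-go decision at 17 patients rests. Followed literally, it makes the only pre-specified efficacy look nearly inert at the null. An inactive combination would go on to 34 patients, each with required pre-treatment and on-treatment biopsies (Sections 5.1 and 6.1). The DSMB would be applying a rule whose properties are not those it was told.

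**Working it through.** **Inputs (all Section 16.4).** Null: P_r = 0.05, P_s = 0.50. Alternatives: P_r = 0.20 or P_s = 0.71, with the other endpoint at its null value. Stage sizes 17 and 17. Final rejection: R ≥ 5 or S ≥ 22 of 34. Overlap P_rs: independence P_r·P_s, maximum min(P_r, P_s), minimum max(0, P_r + P_s − 1).

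**Two bounds by hand**

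- Stopping under the written rule needs 0 responses and at most 3 progression free. P(S ≤ 3 of 17 | 0.50) = (1 + 17 + 136 + 680)/2^17 = 834/131,072 = 0.64%. Early stopping cannot exceed this under any dependence.
- P(0 of 17 responses | 0.05) = 0.95^17 = 41.8%. No rule that continues on one response can stop 52% of the time, whatever the PFS cut-off.

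**Early stopping under the null, written rule**

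- Independence: 0.95^17 × 834/131,072 = 0.4181 × 0.00636 = 0.27%.
- Maximum overlap (P_rs = 0.05): Σ over k = 0–3 of C(17,k)·0.45^k·0.50^(17−k) = 0.47%.
- Minimum overlap (P_rs = 0): Σ over k = 0–3 of C(17,k)·0.50^k·0.45^(17−k) = 0.14%.

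**Full two-stage calculation.** Each patient falls in one of four cells with probabilities P_rs, P_r − P_rs, P_s − P_rs and 1 − P_r − P_s + P_rs. The joint distribution of (R, S) in each stage follows from the multinomial. Rejection is the probability of continuing and then reaching R ≥ 5 or S ≥ 22.

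| Quantity | Stated | Written rule: ≥1 or ≥4 of 17 | ≥2 or ≥10 of 17 |
|---|---|---|---|
| Early stopping, null | ≥ 52% | 0.14–0.47% | 51.6–57.1% |
| Type I error | ≤ 7.9% | 8.23–8.64% | 7.52–7.91% |
| Early stopping, alternative (max) | ≤ 10.7% | 0.16% | 10.73% |
| Power (min) | ≥ 80% | 83.9% | 79.5% |

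With no interim look at all, type I error is 8.51% (independence), 8.23% (maximum overlap) and 8.64% (minimum overlap). To two decimals these equal the written rule's values, so the written look has practically no effect.

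**Other readings of the sentence.** Taking the cut-offs as strict inequalities (2/17 or 5/17) gives early stopping of 1.5–2.3% under the null. Replacing OR by AND gives about 42%, and power at P_s = 0.71 falls to 48–50%. Neither reaches 52%.

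**Which boundary fits the stated figures.** The search covered stage-1 cut-offs of 1–5 responses and 1–17 progression free, with the final rule held as written. Only ≥2 or ≥10 recovers all four stated figures to rounding.

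**Expected sample size under the null** = 34 − 17 × P(early stop). Written rule: 33.9–34.0. Boundary ≥2 or ≥10: 34 − 17 × 0.571 = 24.3 to 34 − 17 × 0.516 = 25.2. The difference is about 9 patients.

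**The case against.** The contradiction itself is hard to dispute, but its framing can be challenged.

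- **The type I excess is small.** It is 0.3–0.7 percentage points, and minimum power under the written rule is 83.9%, above the stated 80%. This stands: on its own the type I part would be minor.
- **The written rule gives some protection against a clearly poor regimen.** Under independence with P_s = 25%, it stops 15% of the time at P_r = 5% and 35% at P_r = 0. With P_s = 20%, the figures are 23% and 55%. This is true, but a minimum of 52% under the null must hold at the boundary, where the rule fails.
- **The match to 2/17 or 10/17 is to rounding only.** 51.6% is not strictly at least 52%, nor 79.5% at least 80%. The printed 1 could be the stopping bound for responses (stop at 1 or fewer), but the printed 4 is neither 9 nor 10, so a simple slip is not demonstrated. The intended rule is an inference; the contradiction does not depend on it.
- **The saving of 9 patients assumes accrual waits** at 17 until 3-month status is known. Section 16.4 describes no pause. If enrolment continues meanwhile, the saving is smaller.
- **Timing matters.** Raising a futility bar after stage-1 results are known would be a data-dependent change. The documents do not give accrual status.

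**Conclusion.** The concern holds and must be fixed. As written, the rule stops with probability 0.14–0.47% at the null boundary against a stated 52% or more, a gap of over 50 percentage points. Type I error is 8.2–8.6% against a stated maximum of 7.9%, exceeded under all three dependence structures. The lost futility protection is the serious part; the type I excess is secondary.

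These results use only the plan's own rates, stage sizes, final rule and dependence structures. The cost of about 9 patients additionally assumes a pause at 17 and comparison with the boundary that matches the quoted figures. That match points to the printed stage-1 cut-offs, rather than the quoted probabilities, as the likely error.

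**What to change.** The sponsor's statistician should check the stage-1 boundary against the design output. If it confirms the match, replace the stage-1 sentence in Section 16.4 with: continue to 34 patients if at least 2 of the first 17 respond or at least 10 of the first 17 are progression free at 3 months; otherwise stop accrual. The final rule and quoted figures can then stay, noting that minimum power is 79.5% before rounding.

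If 1/17 or 4/17 is really wanted, keep it and correct the figures: early stopping under the null below 0.5%, type I error up to 8.6%, power at least 83.9%, and early stopping under an alternative at most 0.2%.

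Either way, say whether accrual pauses at 17 while 3-month status is awaited. The cost is a short amendment to one paragraph, with no added patients or procedures. If stage-1 outcomes are already known, the amendment should say so and justify the change.
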